The model-derived mean placebo-corrected change from baseline in QTc ($\Delta\Delta QTcF$) and corresponding 2-sided 90% confidence intervals (CIs) will be computed at concentrations of interests, eg, expected C_{max} at the CCI [REDACTED]. If the upper bound of the 2-sided 90% interval for the $\Delta\Delta QTcF$ as estimated by the final concentration- ΔQTc model established in this study is <10 msec at the highest clinically relevant exposure, the absence of an effect of sisunatovir on QTc will be concluded. The highest clinically relevant exposure (due to intrinsic and/or extrinsic factors) will be determined later from other studies.

For the secondary objective to determine study sensitivity, the change from baseline QTcF interval will be analyzed using a MMRM model with sequence, period, treatment, time (post-dose timepoint), and treatment by time interaction as fixed effects, participants as random effect, and baseline QTcF as covariate. Estimates of the mean difference between moxifloxacin and placebo at 3, 4, and 5 hrs post-dose and the corresponding two-sided Bonferroni-adjusted 90% CIs (96.7% CIs) will be reported separately. This study will be deemed sensitive to detect QT/QTc prolongation if the lower limit of the Bonferroni-adjusted 90% CI (96.7% CI) of mean difference between moxifloxacin and placebo at any of the 3, 4, or 5 hrs post-dose is greater than 5 msec.

[figure not shown]
Ethical Considerations:

There is no known benefit for healthy participants participating in this trial. This study is designed primarily to investigate the effects of sisunatovir on QTc Interval.

Based on the data from completed Phase 1 and 2 studies, the clinical safety profile of sisunatovir appears to be acceptable. Sisunatovir will be administered in this study at doses that were found to be well tolerated in previous studies.

Moxifloxacin is a fluoroquinolone antibiotic that produces consistent and predictable QT prolongation and a single dose of 400 mg is routinely used as a positive control in Concentration QT/QTc (C-QT) studies.

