4.2. Scientific Rationale for Study Design

This purpose of this study is to assess the effect of sisunatovir on QT interval as recommended by the ICH E14 guideline and in ICH E14 Q&As (R3).⁵ The concentration-QT analysis is defined as the primary analysis in this study and serves as the primary basis for the decision to classify the QT prolongation risk for sisunatovir.

Preliminary CCI [redacted] analysis of SAD and MAD data (C5241001) for sisunatovir suggested that overall, the model predicts CCI [redacted] doses of up to CCI [redacted] mg and CCI [redacted] doses of up to CCI [redacted] mg of RV521 with CCI [redacted] on ECG parameters. The effects of sisunatovir on QT interval was evaluated in Part A (single dose administration) of the study. This part of the study did not include a placebo group, but since the lowest dose (10 mg) resulted in exposure below the limit of detection, the data from this group was used as a surrogate for placebo. A model was built to investigate the effect of RV521 on QTcF at concentrations seen in Part A of the study. In particular, predictions of the effect at the geometric mean of the individual C_{max} values under each dose with quantifiable concentration and at least 6 participants were given together with two-sided 90% confidence intervals. As the results CCI [redacted] any effect of RV521 on CCI [redacted], and, indeed indicate no effect at all, a more in-depth investigation into the appropriateness of the assumption of linearity or absence of PK-PD-hysteresis was not considered necessary. A similar evaluation was performed for data obtained from Part B (placebo controlled, multiple dose administration) and a similar conclusion was reached where no effect of treatment on QTcF was observed.

In order to achieve therapeutic concentrations the current study will dose to steady state, which is achieved after approximately CCI [redacted] so the current study will evaluate

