To increase the confidence that this study has the ability to detect a QTc prolongation in the range of approximately 5 ms, a concurrent positive control will be included to establish assay sensitivity. In this study, moxifloxacin will be used as the active control. Moxifloxacin is a fluoroquinolone antibiotic that produces consistent and predictable QT prolongation and is routinely used as a positive control in TQT studies. Based on recent Pfizer experience from TQT trials conducted at internal CRUs using automated readings, a single 400 mg dose of moxifloxacin produces a maximum mean heart rate-corrected QT interval using Fridericia's correction (QTcF) change from baseline between 7.9 msec and 11.0 msec 2 to 5 hours postdose time points with machine readings. The t_{max} of moxifloxacin is delayed by ≥ 1 hour when administered under fed conditions^{8,9}, with delays in the peak effects on QTc to 4 hours post-dose⁹. Encapsulation of commercially available moxifloxacin tablets to achieve blinding has the potential to have an impact on absorption, therefore encapsulation will not be employed and moxifloxacin will be administered on Day 3 in an open manner. Blood samples from participants randomized to placebo or moxifloxacin will be collected and retained, but will not be routinely analyzed.

All ECG measurements will be performed in triplicate at each nominal sampling time (see [Schedule of Activities](#) and [Electrocardiogram Section 8.3.3](#)). Triplicate measurements are intended to reduce the intrinsic variability and measurement error associated with ECG measurement of the QT/QTc interval. The collection of ECGs at multiple time points is performed to take into consideration the diurnal pattern and variability of QT intervals, dependent upon multiple factors including activity level, postural changes, circadian patterns and food ingestion. The sampling time points have been chosen based on the expected PK profiles of sisunatovir and moxifloxacin. The time to reach maximum concentration (T_{max}) for sisunatovir is approximately 4 to 6 hour postdose based on previous Phase 1 and 2 studies

(Summary of sisunatovir Pharmacokinetics Section 8.5). This schedule will also allow peak QT effects with moxifloxacin, to be captured.⁷

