9. STATISTICAL CONSIDERATIONS

Detailed methodology for summary and statistical analyses of the data collected in this study is outlined here and will be further detailed in the SAP, which will be maintained by the

sponsor. The SAP may modify what is outlined in the protocol where appropriate; however, any major modifications of the primary endpoint definitions or their analyses will also be reflected in a protocol amendment.

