9.1. Statistical Hypothesis

9.1.1. Primary Endpoint

Concentration-QTc analysis will be used to assess if sisunatovir at maximum concentrations (C_{max}) at the **CCI** has clinically relevant effect on the QTc interval at one sided $\alpha = 0.05$ level without multiplicity adjustment. After a final concentration- ΔQTc model has been established, denote the population mean of model predicted placebo-corrected $\Delta QTcF$ ($\Delta\Delta QTcF$) at the C_{max} of a dose of interest as μ_{cmax} , the null hypothesis of sisunatovir having a positive QTc effect and the alternative hypothesis of sisunatovir having a negative QTc effect at the dose of interest can be expressed as the following:

$$H_0: \mu_{cmax} \geq 10 \text{ msec}$$

$$H_a: \mu_{cmax} < 10 \text{ msec}$$

The lack of effect of sisunatovir on QTc intervals will be concluded if the upper bound of the 2-sided 90% CI for the $\Delta\Delta QTcF$ estimated by the final concentration- ΔQTc model is < 10 msec at the highest clinically relevant exposure.

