9.1.2. Assay Sensitivity

The assay sensitivity is tested at 3, 4 and 5-hours post-dose of positive control, moxifloxacin, on Day 3 simultaneously at one-sided $\alpha = 0.05$ level with Bonferroni correction of $\alpha/3$ for multiple assessments. Denote the population mean of change from baseline in QTcF of moxifloxacin and placebo at 3, 4, or 5-hr post-dose as $\mu(M)$ and $\mu(P)$, respectively, the statistical hypotheses are:

$$H_0: \mu(M) - \mu(P) \leq 5 \text{ msec}$$

$$H_a: \mu(M) - \mu(P) > 5 \text{ msec}$$

The study will be deemed adequately sensitive to detect QT/QTc prolongation if any of the lower limits of the two-sided Bonferroni-adjusted 90% CI (96.7% CI) for mean differences between moxifloxacin and placebo at any of the 3, 4 and 5-hr post-dose, respectively, are greater than 5 msec.

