9.5. Sample Size Determination

A sample size of 42 (7 per sequence) participants will provide approximately 99% power to detect a 5 msec difference between moxifloxacin and placebo at historical moxifloxacin

Tmax (3 hour) to demonstrate the study sensitivity, if the expected mean difference between moxifloxacin and placebo is no less than 10 msec at Tmax.

This calculation used a 1-sided 5% paired t-test and assumed a conservative estimate of common intra-subject standard deviation of 5.61 msec for the change from baseline in QTcF, based on a previous study (C5241001). Previous PCRU TQT studies (A4301023, A3921028, A5761016, A5951151, A5271032, A4251025, A7691017 and B1811062) had an average dropout rate of approximately 2%. Assuming a 2% dropout rate, 41 participants would provide approximately 99% power to demonstrate the study sensitivity.

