## 2. INTRODUCTION

*This study is designed as a thorough QT study (TQT) to assess the effect of sisunatovir on time from the beginning of the QRS complex to the end of the T wave on the electrocardiogram (ECG), corresponding to electrical systole (QT interval) as recommended by the International Council for Harmonisation (ICH) E14 guideline and in Q&As (R3).*

This statistical analysis plan (SAP) provides the detailed methodology for summary and statistical analyses of the data collected in Study C5241015. This document may modify the plans outlined in the protocol; however, any major modifications of the primary endpoint definition or its analysis will also be reflected in a protocol amendment.

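### A conclusion of no QTc effect does not depend on the moxifloxacin assay-sensitivity criterion being met

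*Protocol*

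**What the plan says.** The negative conclusion is stated in five places: Protocol 1.1 (Statistical Methods), 9.1.1 and 9.3.2, and SAP 5.1.1 and 5.2.3. Protocol 9.1.1 and SAP 5.1.1 read "The lack of effect of sisunatovir on QTc intervals will be concluded if the upper bound of the 2-sided 90% CI" is under 10 msec. The other three apply the same test and end with "the absence of an effect of sisunatovir on QTc will be concluded". Protocol 4.2 says that the concentration-QT analysis "serves as the primary basis for the decision to classify the QT prolongation risk for sisunatovir".

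Assay sensitivity is a secondary objective with its own rule in the synopsis, Protocol 9.1.2 and SAP 5.1.2 and 6.2.2: "The study will be deemed adequately sensitive to detect QT/QTc prolongation if any of the lower limits" of the 96.7% intervals for moxifloxacin minus placebo at 3, 4 or 5 hours exceeds 5 msec. Protocol 4.2 gives the reason for the positive control: "To increase the confidence that this study has the ability to detect a QTc prolongation in the range of approximately 5 ms". Protocol 9.5 sizes the trial on this comparison and states no power for the primary rule.

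**The concern.** The primary test favours a small estimate. Anything that systematically shrinks measured QTc effects makes an upper bound below 10 msec easier to reach, and the positive control is the study's means of revealing such shrinkage. Yet the plan attaches no consequence to a missed criterion. If moxifloxacin failed and the sisunatovir bound were under 10 msec, the written rule would still declare absence of an effect.

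A missed criterion does not prove that the assay was insensitive. It does mean that a low upper bound is not enough to call the result a true negative. How such a result is read should be settled in advance, because the sponsor may review unblinded data during the study (Protocol 6.4.3, 9.4) and the final concentration-QTc model may change after exploratory plots (SAP 5.2.3).

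**Working it through.** **1. The text.** In all five statements the 10 msec bound is the only condition. The assay-sensitivity statements stop at declaring the study sensitive; none has a failure branch or refers to the primary conclusion. SAP 2.1 lists no modification that would supply the link.

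**2. The plan's power figure.** Protocol 9.5: "This calculation used a 1-sided 5% paired t-test and assumed a conservative estimate of common intra-subject standard deviation of 5.61 msec". Other inputs from that section: 42 participants (41 after 2% dropout), expected difference 10 msec, threshold 5 msec.

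- SD of a paired difference = 5.61 × √2 = 7.93 msec
- SE at n=41 = 7.93 / √41 = 1.239 msec
- Noncentrality = (10 − 5) / 1.239 = 4.04
- Power, one-sided 5%: 99.0% (n=41), 99.1% (n=42)

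The stated 99% reproduces, but it describes one unadjusted test at 3 hours. For the adopted rule:

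- Interval level = 1 − 2 × 0.05/3 = 96.7%
- t(0.98333, 40 df) = 2.204; half-width = 2.204 × 1.239 = 2.73 msec
- Observed difference needed at one time point = 5 + 2.73 = 7.73 msec
- Power at one time point for 10 msec: 96.3% (n=41), 96.7% (n=42)

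**3. How often the criterion is missed.** Simulation of the any-of-three rule, n=41, 40,000 trials per cell. Assumptions: peak at 4 h, 3 h and 5 h lower by 0 to 1 msec, between-time correlation 0 to 0.8.

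| True peak difference (msec) | Criterion missed |
|---|---|
| 11 | 0.0% to 0.3% |
| 10 | 0.0% to 2.9% |
| 9 | 0.3% to 13.5% |
| 7.9 | 8.4% to 41.8% |

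The 7.9 msec is the low end of the historical range in Protocol 4.2. That range is a change from baseline and is not stated to be placebo-corrected, so using it as a difference from placebo is an assumption.

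**4. How often the gap would bind.** The sisunatovir bound must also be under 10 msec. The documents give no standard error for the concentration-QTc model, so a paired comparison at 4 h stands in: half-width = t(0.95, 40 df) × SE = 1.684 × 1.239 = 2.09 msec. The comparisons share the placebo period.

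| True sisunatovir effect (msec) | Bound <10 | Criterion missed and bound <10, moxifloxacin peak 10 | Same, peak 7.9 |
|---|---|---|---|
| 0 | 100% | 0% to 2.7% | 8.8% to 41.7% |
| 5 | 99% | 0% to 2.8% | 8.5% to 41.5% |
| 7 | 77% | 0% to 2.8% | 7.6% to 37.5% |
| 10 | 5% | 0% to 0.7% | 0.8% to 3.9% |

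**5. What the missing condition could let through.** Assume that the study registers a fraction f of every true effect, and that the true moxifloxacin and sisunatovir effects are both 10 msec. Concluding absence is then wrong.

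| f | Stated rule concludes absence | With the added condition |
|---|---|---|
| 1.0 | 4.9% to 5.1% | 4.2% to 5.0% |
| 0.8 | 47.2% to 48.0% | 23.1% to 42.7% |
| 0.6 | 93.5% to 93.8% | 8.4% to 22.0% |
| 0.5 | 98.9% to 99.1% | 1.9% to 4.8% |

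Steps 3 to 5 use paired t intervals, as Protocol 9.5 does, not the MMRM or the concentration-QTc model.

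**The case against.** The case against concedes the text and the arithmetic but disputes the size and the remedy.

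- **Most of the joint probabilities are not wrong conclusions.** With a true sisunatovir effect of 0 to 5 msec, the alternative hypothesis is true. Without attenuation the stated rule keeps its 5% error. This stands: those figures count conclusions that lack demonstrated sensitivity, not false ones.
- **The 99% needs a halving of every effect.** Nothing in the documents suggests this, ordinary noise widens the interval and makes the rule harder to pass, and Protocol 2.2.4 reports no significant prolongation in earlier concentration-QT analyses. It is an illustration, not a forecast, but such a loss is what a positive control is there to detect.
- **The condition helps only partly when attenuation is moderate.** True: at f=0.8 much of the error remains, and a further run at f=0.9 gave about 19% falling to 13% to 19%.
- **The failure rates depend on inputs.** The plan calls 5.61 msec conservative. With an assumed SD of 4.5 msec, failure at 7.9 msec is 5% to 23%, against 17% to 42% at 5.61 (correlation 0.4 to 0.8). Zero correlation between times sharing one baseline is implausible, so the low ends of the ranges are optimistic.
- **The intent can be inferred.** Protocol 4.2 calls the concentration-QT analysis the primary, not the sole, basis, and a report would show both results; one sentence after 9.1.2 might do. But the five statements would still make the bound sufficient, and a prespecified decision rule should not rest on inference.

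These points limit the size of the problem. They do not supply the missing condition.

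**Conclusion.** The concern holds. As written, an upper bound under 10 msec is sufficient to conclude absence of an effect whether or not assay sensitivity is shown, although the positive control was included, and the trial sized, to show it.

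Under the planned 10 msec moxifloxacin difference the gap would seldom bind (at most about 3%). It could bind often if the difference were near 7.9 msec. The missed-criterion rates are upper limits on how often it binds. The harm when it binds depends on systematic attenuation, which is assumed here. The reading of the text is secure; the probabilities rest on the paired-t stand-in and the stated correlations, off-peak drops and SD. The change should be made: the gap lies in the primary decision rule and is cheap to close.

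**What to change.** In Protocol 1.1, 9.1.1 and 9.3.2 and SAP 5.1.1 and 5.2.3, replace the single condition with wording such as:

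> Absence of an effect is concluded only if the upper bound is <10 msec and the assay-sensitivity criterion (Protocol 9.1.2 / SAP 5.1.2) is met. If the criterion is not met, the upper bound is reported with the statement that assay sensitivity was not demonstrated and that absence of an effect is not concluded from this study alone.

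A bound of 10 msec or more is read as now. Show the moxifloxacin-placebo differences and intervals already planned in SAP 6.2.2 alongside. In the synopsis and Protocol 9.5, add power for the any-of-three rule: about 97% to 100% at 10 msec with n=41, so the sample size need not change.

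**Cost.** No new data, analysis or alpha: a second condition cannot raise the type I error. Protocol 9 requires that "any major modifications of the primary endpoint definitions or their analyses will also be reflected in a protocol amendment", and SAP 2 says the same. Protocol 10.1.1 requires IRB/EC approval, and health authority approval if the amendment is substantial. The sponsor accepts a risk of being unable to conclude absence: about 0% to 3% under the planned effect, and about 8% to 42% if the true moxifloxacin difference is 7.9 msec.

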9.1.2. Assay Sensitivity

The assay sensitivity is tested at 3, 4 and 5-hours post-dose of positive control, moxifloxacin, on Day 3 simultaneously at one-sided $\alpha = 0.05$ level with Bonferroni correction of $\alpha/3$ for multiple assessments. Denote the population mean of change from baseline in QTcF of moxifloxacin and placebo at 3, 4, or 5-hr post-dose as $\mu(M)$ and $\mu(P)$, respectively, the statistical hypotheses are:

$$H_0: \mu(M) - \mu(P) \leq 5 \text{ msec}$$

$$H_a: \mu(M) - \mu(P) > 5 \text{ msec}$$

The study will be deemed adequately sensitive to detect QT/QTc prolongation if any of the lower limits of the two-sided Bonferroni-adjusted 90% CI (96.7% CI) for mean differences between moxifloxacin and placebo at any of the 3, 4 and 5-hr post-dose, respectively, are greater than 5 msec.

9.2. Analysis Sets

For purposes of analysis, the following analysis sets are defined:

Participant Analysis Set	Description
Enrolled	“Enrolled” means a participant’s, or their legally authorized representative’s, agreement to participate in a clinical study

Participant Analysis Set	Description
	following completion of the informed consent process and randomization. A participant will be considered enrolled if the informed consent is not withdrawn prior to participating in any study activity after screening. Potential participants who are screened for the purpose of determining eligibility for the study, but do not participate in the study, are not considered enrolled, unless otherwise specified by the protocol.
ECG analysis set	All participants randomized and treated who have at least 1 post-dose ECG measurement in at least 1 period. Analysis sets may contain different numbers of participants for different ECG parameters based on availability of data. Participants will be analyzed according to the product they actually received.
Concentration-QTc analysis set	The concentration QTc analysis population is defined as all participants randomized and treated with sisunatovir or placebo who have at least 1 pair of time-matched post-dose QT and sisunatovir plasma concentration values in at least 1 period of the study. For placebo treatment, the concentration of is set to 0.
PK Concentration analysis set	All participants randomly assigned to study intervention and who take at least 1 dose of study intervention and in whom at least 1 concentration value can be reported.
PK Parameter analysis set	All participants randomly assigned to study intervention and who take at least 1 dose of study intervention and in whom at least 1 of the PK parameters of interest can be reported.
Safety analysis set	All participants randomly assigned to study intervention and who take at least 1 dose of study intervention. Participants will be analyzed according to the product they actually received.

9.3. Statistical Analyses

The SAP will be developed and finalized before any analyses are performed and will describe the analyses and procedures for accounting for missing, unused, and spurious data. This section is a summary of the planned statistical analyses of the primary and secondary endpoints.

9.3.1. General Considerations

Details of the analyses will be provided in the SAP.

9.3.1.1. Derivation of ECG Parameters Prior to Analyses

The average of the triplicate ECGs collected at each time point according to the [SoA](#) will be calculated and used in PK/PD modeling, statistical analyses, and/or descriptive summaries.

The QTcF is defined as Fridericia's heart rate correction, obtained using the formula:

- $QTcF \text{ (msec)} = QT \text{ (msec)} / (RR)^{1/3}$ where $RR(\text{sec}) = 60/\text{HR}$ (if not provided)

The QTcB is the Bazett's heart rate correction, obtained using the formula:

- $QTcB(\text{msec}) = QT(\text{msec}) / (RR)^{1/2}$ where $RR(\text{sec}) = 60/\text{HR}$ (if not provided)

The baseline of ECG parameters will be defined as the mean of the 3 averages of the triplicate measurements taken at the following 3 time points (approximately 40 min, 25 min, and 10 min before pre-dose meal) before dosing on Day 1 within each period. Changes from baseline ECG parameters, including changes from baseline in QTcF, uncorrected QT, QTcB, PR, QRS, and heart rate, will be calculated for each participant and treatment at each post-dose timepoint on Day 3 and 4 within each period.

The maximum absolute post-dose value and the maximum increase from baseline for QTcF, QTcB, PR, and QRS intervals will be determined for each participant and treatment. When there is no increase from baseline over the respective period, the minimum decrease will be taken.

9.3.1.2. ECG Data Summaries

Mean baseline and changes from baseline for QTcF, QTcB, QT (uncorrected), PR, QRS and heart rate will be calculated for each participant and summarized descriptively (N, mean, standard deviation [SD], median, minimum and maximum) by treatment and time postdose.

Placebo-corrected change from baseline for QTcF, QT (uncorrected) and heart rate differences will be summarized (N, mean, 90% CI) and plotted (mean) for each treatment and time point postdose.

Categorization of HR, QRS, and PR intervals will be described in the SAP. Categorization of maximum QTc will be provided for QTcF by treatment using the following criterion.

Absolute Maximum (msec)	<450	450 to <480	480 to <500	≥500
Maximum Increase from Baseline (msec)	<30	30 to <60	>60	

If any of the 3 individual ECG tracings has a QTcF value ≥500 msec, but the mean of the triplicates is < 500 msec, the data from the participant's individual tracing will be described in a safety section of the study report in order to place the ≥500 msec value in appropriate clinical context. However, values from individual tracings within triplicate measurements

PFIZER CONFIDENTIAL

CT02-GSOP Clinical Pharmacology Protocol Template (01 April 2022)

Page 68

that are ≥ 500 msec will not be included in the categorical analyses unless the average from the triplicate measurements is also ≥ 500 msec.

